Investigators will insert 150 restorations. Carbide finishing burs (Midwest 7402, OS 1, OS 2) will be used to remove gross excess, followed by finishing strips and disks (Sof-Lex, 3M, St Paul, MN), and the Enhance system (Dentsply Caulk, Milford, DE). All polishing will be done at slow speed with water spray. After removing the rubber dam the occlusion will be adjusted. Each restoration will be evaluated directly and indirectly at The direct clinical evaluations will be made using the checklist in table one, a modification of the United States Public Health Services (USPHS) guidelines.

Each restoration will be evaluated for anatomic form, color match, marginal integrity, marginal discoloration, proximal contact, polishability, caries, sensitivity, gingival index. Indirect wear measurements will be made on casts from impressions made at baseline, 12 and 24 month recall visit

Two of the trained and calibrated evaluators (Drs [name], [name], [name], [name] and [name]) who have not placed restorations, will perform post-restorative evaluation at baseline, 6 months, 12 months and 24 months. A consensus will be reached if both evaluators disagree on the restorations' direct assessment. [name] will provide retraining any time throughout the study upon evaluator's request.

Study Visits

Subjects will be evaluated at the Eastman Institute for Oral Health General Dentistry Department. Study visits at one week, 6, 12 and 24 months may be combined with routine dental care visits.

Screening:

Subjects will be screened for study eligibility. Two bitewing radiographs will be taken of teeth in need of restorations.

If a subject is eligible, the informed consent process will initiate. Subject will be given a consent form by a member of the study team and discuss study procedures. Subjects will be informed about the option of taking the consent form home and schedule an appointment at their convenience as well as that their participation is strictly voluntary and participation will not affect their care.

If the subject wishes to participate in the study a copy of the consent form will be given and pre-operative assessments indicated on schedule of events (appendix 1) will be administered. If the subject satisfies inclusion criteria for the study and wishes to receive the restoration at this visit a restoration or two restorations will be placed by one of the sub-investigators. Subjects can choose to schedule a separate appointment for restorations placement and no additional study procedure will be required at the restorative visit.

Baseline (one week after the restorations)

Study procedure:

Subject's restorations will be evaluated by two investigators other than the investigator who placed the restorations for the following:

- anatomic form,
- color match,
- marginal integrity,
- marginal discoloration,
- proximal contact,
- polishability
- caries.
- sensitivity
- Gingival index – (a dental probe will gently stimulate gingival tissues around the two restored teeth).
- Impressions for wearing and contact assessments will be taken. – A soft material is placed on the subject's upper or lower dentition or both (depending on the location of restored teeth). As the material hardens will leave a negative print of the subject's dentition. A stone material is then poured into the impression resulting in a cast which will allow restorations' wearing and contact measurements.
- Two radiographs will be taken. These radiographs are taken in addition to the screening radiographs as they will provide a post-restorative baseline.

- Photographs of restoration(s) will be taken with a digital camera. Subjects will be identified according to their assigned subject number.

Standard of care: Patient is scheduled a week after a restoration is placed for follow up. Radiographs may be taken for possible overhang and/or patient's complaints. Patients will be asked to report complaints and possible adverse events.

6 months follow-up

Study procedure:

Subject's restoration (s) will be evaluated by two investigators other than the investigator who placed the restorations for the following:

- anatomic form,
 - color match,
 - marginal integrity,
 - marginal discoloration,
 - proximal contact,
 - polishability
 - caries.
 - Photographs of both restoration
 - Gingival index score will be collected.
-
- Vitality – an electrical pulp tester is placed on the tooth in need of restoration and an adjacent tooth to evaluate level of vitality. A drop of toothpaste or the subject's saliva is used as a conductor of electricity. Subjects may experience a tingling sensation.
 - Sensitivity - (a cotton swab embedded with a cold solution will be placed on the tooth surface to assess sensitivity response)

Standard of care:

Patients will be asked to report complaints and possible adverse events.

12 months follow-up

Study procedure:

Subject's restoration(s) will be evaluated by two investigators other than the investigator who placed the restorations for the following:

- anatomic form,
- color match,
- marginal integrity,
- marginal discoloration,
- proximal contact,
- polishability
- caries.
- Sensitivity

- Gingival index score will be collected.
- Vitality test
- Impressions for wearing and contact assessments will be taken (See Baseline)
- Photographs of both restorations will be taken
- 2 periapical radiographs of restored teeth will be taken to evaluate possible apical pathology.

Standard of care

Bitewing in addition to the two periapical radiographs will be taken for annual dental caries screening.

Subjects will be asked to report complaints and adverse events.

24 months follow-up

Study procedure:

Subject's restoration(s) will be evaluated by two investigators other than the investigator who placed the restorations for the following:

- anatomic form,
- color match,
- marginal integrity,
- marginal discoloration,
- proximal contact,
- polishability
- caries.
- Sensitivity
- Gingival index score will be collected
- Vitality test
- Impressions for wearing and contact assessments will be taken (See baseline).
- Photographs of both restorations will be taken
- 2 periapical radiographs of restored teeth will be taken to assess apical pathology.
- Patients will be asked to report possible adverse events.

Standard of care

Bitewing in addition to periapical radiographs will be taken for dental annual screening.

Subjects will be asked to report complaints and adverse events.

Cost

Subjects and/or dental insurance will be responsible for the cost associated with standard of care of diagnostic procedures. In the event that alternative treatment is indicated, such as replacing a failed restoration, sponsor will be responsible for the cost associated with the procedure. Diagnostic radiographs for study requirements will be taken at no charge to the subjects.

9. Payment for Participation.

Subject will receive the following payments.

baseline - \$20

6 months – \$40

12 months – \$50

24 months – \$70

Subjects will receive a total of \$180.00

Evaluators will be calibrated.

[name] will conduct preclinical sessions to train clinicians by preparing and restoring at least two extracted teeth mounted in stone. Each tooth will be prepared and restored according to the guidelines above and will also standardize restoration placement among the clinicians (Drs [name], [name], [name] and [name]). [name] will also conduct a clinical training session to train clinician evaluators (Drs [name], [name], [name] and [name]) to conduct baseline and recall measurements using the standards, appendix 1. Scores for each evaluator will be compared to other evaluators and inter-evaluator comparisons made. The trained evaluators will independently evaluate each restoration in our clinical study and a forced consensus obtained if necessary. A kappa value of 0.8 of all criteria is expected after calibration of the examiners

Data Analysis:

Restorations placed using each composite will be analyzed. The categorized clinical assessment data (color, marginal discoloration, secondary caries, anatomic form, marginal adaptation) will be summarized by computing percentages for each category and used to describe any trends noted in the performance of the groups. In the analysis of categorical data of anatomic form, color match, marginal integrity, marginal discoloration, proximal contact, polishability, caries, sensitivity, and gingival index, the frequency distribution over various categories will be calculated and reported. A sample size of 100 restorations in 50 subjects is not based on a statistical plan, but rather on guidelines put forth by the American Dental Association for obtaining approval as an amalgam replacement for posterior restorations. The guidelines specifically call for an evaluation of a minimum of 30 restorations in a minimum of 20 subjects at 18 months. Taking subject attrition into account that forms the 2 and 3 year requirements.

The primary efficacy variables are based on ADA guidelines for acceptance and include the direct assessments of anatomic form, color match, marginal integrity, marginal discoloration, proximal contact, polishability, caries, sensitivity, and gingival index, and periapical pathology. Scores for primary efficacy variables will be summarized and displayed using descriptive statistics. The success criteria for the primary efficacy variables for passing the ADA requirements for acceptance at 18 months, namely;

Color Match – no more than 10% scores of C

Marginal Discoloration – no more than 10% scores of C

Marginal Integrity – no more than 10% scores of C – no scores of D

Caries – an incidence of no greater than 5%

Proximal Contour – not less than 95% showing no observable evidence of broadening of contact

Wear– no more than 50 microns

The ADA guidelines do not specify requirements for Proximal Contacts, Vitality, Sensitivity or Periapical Pathology. Success criteria for these parameters will be based on comparisons to incidences reported in the literature. Secondary efficacy variables include direct assessments of Anatomic Form and the Gingival Index, and the indirect assessment of occlusal contact. Scores will be summarized and displayed using descriptive statistics. Success criteria will be based on comparisons to reports in the literature. Safety variables include adverse events, unanticipated adverse device effects, and complaints. Descriptions of occurrences, incidence, severity and required treatments will be summarized and tabulated where appropriate.

Criteria for evaluation:

Modified USPHS criteria will be used to assess individual restorations.

Times of evaluation: Baseline, 6 months, 12 months, 24 months

Unanticipated Adverse Device Effects

Unanticipated adverse device effect means any serious adverse effect on health or safety or any life-threatening problem or death caused by, or associated with, a device, if that effect, problem, or death was not previously identified in nature, severity, or degree of incidence in the investigational plan or application (including a supplementary plan or application), or any other unanticipated serious problem associated with a device that relates to the rights, safety, or welfare of subjects.

MONITORING The sponsor may monitor this trial at timely intervals for compliance with this protocol, applicable FDA regulations and any conditions of approval imposed by reviewing the IRB. This trial will also be monitored for safety related issues to determine whether any unreasonable risk to subjects develops.

ACCESS TO RECORDS

Investigators will permit monitoring, audits and regulatory inspections and will provide direct access to study related documentation.

REPORTING REQUIREMENTS

- Unanticipated Adverse Device Effects will be reported to the sponsor and the reviewing IRB as soon as possible, but no later than within 10 working days.
- Withdrawal of IRB approval will be reported to the sponsor within 5 working days. Any use of the device in humans without informed consent will be reported to the sponsor within 5 working days. Upon request, reports of complaints and adverse events will be provided to the sponsor.

Problem cases

Where a study restoration has failed this will be recorded on the Failed Restoration An alternative treatment (of a different composite resin restorative and bonding system, or other direct restorative system, at the discretion of the clinician) will be offered to the patient and a record made in the patient's notes. Neither the patient, nor the clinician will pay for this further treatment. [name], Director of Clinical Research at Dentsply Caulk must be notified that an alternative treatment has been necessary and requires

payment by the sponsor. Factors determining restoration failure or success will be the result of evaluators' assessment criteria listed on Appendix 2.

Restorative materials will have the same tooth color, consistency and odor.

Adverse Events

Any adverse reaction to the treatment provided as part of the study will be fully investigated and recorded on the Adverse Event Record Form including details of the appropriate clinical action taken, and promptly reported to the Investigational Review Board. [name], Director of Clinical Research, Dentsply Caulk will be the contacted at [contact]). In the event of an adverse reaction to the restorative material, any indemnity will be borne by Dentsply Caulk, in accordance with the research contract. Any decision as to whether to prematurely stop the study will be taken jointly by the PI, IRB and Dentsply Caulk. The IRB will be updated by the PI regarding adverse events according to the IRB reporting guidelines.

Reports to sponsor

The PI will prepare and submit a report to the sponsors following completion of the 6 month, 12 month and 24 month recalls

Publication of findings

The investigators will be entitled to publish the findings of the evaluation; the data may also be presented as an abstract or oral presentation at an appropriate Dental Research meeting. Any manuscript, abstract or other communication prepared for submission or public presentation should be submitted to the sponsors for comment as stated in the contract. The data will also be communicated internally at Caulk to appropriate members of the Business Team and Professional Services, Marketing, Regulatory and R & D personnel.

“Clinical Evaluation of an Experimental Urethane Dimethacrylate Resin Based Composite”

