PROTOCOL

**“Clinical Evaluation of an Experimental Urethane Dimethacrylate
Resin Based Composite”**

NCT0201882

Purpose: This double blind randomized, controlled prospective clinical trial will compare the clinical success of two tooth colored resin composite dental filling materials- TPH3 (Dentsply Caulk) and an experimental urethane dimethacrylate resin based composite resin (Dentsply Caulk) for wear resistance, staining and marginal seal using modified Ryge criteria to evaluate the posterior restorations for 24 months in duration.

Study Objectives

The purposes of this clinical trial is to evaluate two composite resins used to restore Class I and Class II cavities in teeth of adults. The clinical study will evaluate the resin composite restorations placed in Class I and Class II cavity preparations for anatomic form, color match, marginal integrity, marginal discoloration, proximal contact, polishability, caries, sensitivity, gingival index, staining, wear, and thermal response for 24 months..

Study Design

The study will be double blind randomized, controlled clinical evaluation of similar sized class I and class II with both dental restorative materials placed in a single patient. Both esthetic restorative materials will be bonded with a single bonding agent Prime and Bond Elect (Dentsply Caulk).

Randomization: teeth that require restorations and satisfy the inclusion criteria parameters will be randomly selected. Code R will be assigned to the most anterior tooth or located on the right. Code T will be assigned to the most posterior tooth or located on left. See randomization scheduled (appendix 3). Sponsor will blind both esthetic bonding materials and label them code R and code T.

The study will be conducted in the Division of General Dentistry at Eastman Institute for Oral Health University of Rochester. The study will evaluate the pair of composite resin restorations over a two year period.

50 adult patients aged 18 - 85 yearsold will be recruited into the study. Based on previous clinical trials, the average attrition rate for a two year clinical trial is approximately 10% per year. To assure that 30 restorations per material are available at the three year recall, 100 restorations (50 of each material) will be placed assuming a 20% attrition rate.

Investigators

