Each restoration will be evaluated for anatomic form, color match, marginal integrity, marginal discoloration, proximal contact, polishability, caries, sensitivity, gingival index. Indirect wear measurements will be made on casts from impressions made at each recall and baseline.

Two of the trained evaluators (Drs [name], [name], [name] and [name]) who have not placed restorations, will perform post-restorative evaluation at baseline, 6 months, 12

months and 24 months. A consensus will be reached if both evaluators disagree on the restorations' direct assessment. [name] will provide retraining any time throughout the study upon evaluator's request.

Study Visits

Subjects will be evaluated at the Eastman Institute for Oral Health General Dentistry Department. Study visits at 6, 12 and 24 months may be combined with routine dental care visits.

Screening:

Subjects will be screened for study eligibility. Two bitewing radiographs will be taken of teeth in need of restorations.

If a subject is eligible, the informed consent process will initiate. Subject will be given a consent form by a member of the study team and discuss study procedures. Subjects will be informed about the option of taking the consent form home and schedule an appointment at their convenience as well as that their participation is strictly voluntary and participation will not affect their care.

If the subject wishes to participate in the study a copy of the consent form will be given and pre-operative assessments indicated on schedule of events (appendix 1) will be administered. If the subject satisfies inclusion criteria for the study and wishes to receive the restoration at this visit, the study coordinator will assign products code according to subject number listed on the randomization list (appendix 3) and restorations will be placed by one of the sub-investigators. Subject can choose to schedule a separate appointment for restorations placement and no additional study procedure will be required at the restorative visit.

Baseline (one week after the restorations)

Study procedure:

Subject's restorations will be evaluated by two investigators other than the investigator who placed the restorations for the following:

- anatomic form,
- color match,
- marginal integrity,
- marginal discoloration,
- proximal contact,
- polishability
- caries.
- sensitivity
- Gingival index – (a dental probe will gently stimulate gingival tissues around the two restored teeth).

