C =	There is visual evidence of marginal discoloration at the junction of the tooth structure and the restoration that has penetrated along the restoration in a pulpal direction.

Proximal Contacts	
A =	Tight proximal contacts evaluated with dental floss.
B =	Proximal contacts are weak but present.
C =	No proximal contacts but not visibly open.
D =	Visibly open contacts.

Polishability	
Alpha=	Smooth & highly shiny, similar to enamel
Bravo 1=	Smooth & satin, highly reflective
Bravo 2=	Smooth & shiny but not highly reflective
Charlie=	Rough & shiny, satin, somewhat reflective
Delta=	Rough & dull or satin, not reflective
Eta=	Unacceptable polish

Caries	
A =	Absent
B =	Present

Gingival Index	
0 =	Normal gingival.
1 =	Mild inflammation, slight change in color, slight edema, no bleeding on probing.
2 =	Moderate inflammation, redness; edema and glazing; bleeding on palpation.
3 =	Severe inflammation, marked redness and edema, ulceration, tendency to spontaneous bleeding.

Appendix 3

Randomized list

Subject

#	Code R	Code T
1	T	R
2	R	T
3	R	T
4	R	T
5	T	R
6	T	R
7	R	T
8	R	T
9	R	T
10	R	T
11	R	T
12	T	R
13	T	R
14	T	R
15	T	R
16	T	R
17	T	R
18	R	T
19	R	T
20	R	T
21	R	T
22	T	R
23	T	R
24	R	T
25	R	T
26	T	R
27	R	T
28	T	R
29	T	R
30	R	T
31	T	R
32	R	T
33	R	T
34	T	R
35	R	T

Place code **R** on most anterior tooth or on the **left** side of the mouth

Place code **T** on most posterior or on the **Right** side of the mouth

36	T	R
37	R	T
38	T	R
39	R	T
40	T	R
41	R	T
42	R	T
43	T	R
44	R	T
45	R	T
46	R	T
47	T	R
48	T	R
49	T	R
50	T	R

PROTOCOL Addendum

**“Clinical Evaluation of an Experimental Urethane Dimethacrylate
Resin Based Composite”**

Purpose: This addendum protocol is a controlled prospective clinical trial to evaluate and compare the clinical success of an additional investigational tooth colored resin composite dental filling material, EsthetX HD (Dentsply/Caulk), to TPH3 (Dentsply Caulk) and to an experimental urethane dimethacrylate resin based composite resin (Dentsply Caulk). Comparison of EsthetX HD (Dentsply/Caulk) to the resin composite materials used in the original protocol is necessary in order to evaluate its clinical performance. Using the modified Ryge criteria, EsthetX HD (Dentsply/Caulk) restorations will be evaluated for wear resistance, staining and marginal seal during a 24 month period.

Study Objectives

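### The addendum describes no masking for its single-material EsthetX HD cohort, yet compares it with two materials scored double blind under codes, so part of any described difference could come from assessment conditions

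*Combined protocol and SAP*

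**What the plan says.** The original protocol's Purpose states: "This double blind randomized, controlled prospective clinical trial will compare the clinical success of two tooth colored resin composite dental filling materials". Its Study Design adds: "Sponsor will blind both esthetic bonding materials and label them code R and code T". In its Screening section, "the study coordinator will assign products code according to subject number listed on the randomization list". The two original materials are therefore placed and scored under codes.

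The addendum's Purpose reads: "This addendum protocol is a controlled prospective clinical trial to evaluate and compare the clinical success of an additional investigational tooth colored resin composite". It goes on to say that EsthetX HD must be compared with both original materials if its performance is to be judged. Neither its Purpose nor its Study Design claims blinding or randomisation. The sponsor's coding step is gone. Where the original Screening text assigns a code, the addendum says only that "a restoration or two restorations will be placed by one of the sub-investigators".

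The addendum's Subject Population section says that enrolment for the two original materials is closed, that those subjects are in follow-up, and that 50 further subjects will be recruited. Trained and calibrated evaluators who placed no restorations "will perform post-restorative evaluation at baseline, 6 months, 12 months and 24 months". The addendum does not say what these evaluators, or the readers of casts and photographs, are told about material or cohort.

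**The concern.** Several direct assessments rest on visual judgement, color match most clearly, and two evaluators settle any disagreement by consensus. If evaluators know the material in one group and see only codes in the others, a shared expectation can move borderline grades in one group alone. Adjusting for patient or tooth characteristics cannot remove this, because it lies in the measurement and not in the case mix. What is at stake is the comparison that the addendum calls necessary. A separate and narrower question is whether knowledge of the material affects EsthetX HD's results against the fixed acceptance limits in Data Analysis.

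**Working it through.** **1. Masking elements side by side.**

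| Element | Original protocol | Addendum |
|---|---|---|
| Design label (Purpose, Study Design) | Double blind, randomised, controlled | Controlled only |
| Sponsor coding of materials | Codes R and T | Not described |
| Code assigned before placement (Screening) | By the coordinator, from a list | Step absent |
| Randomisation list | Appendix 3 | None |
| Schedule row for assignment and randomisation (Appendix 1) | Present | Present, with no matching procedure |
| Evaluator is not the placer | Yes | Yes |
| Calibration target | Kappa 0.8 | Kappa 0.8 |
| Materials look alike (Problem cases) | Stated | Stated |

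**2. Does cohort membership reveal the material?** The addendum plans 50 restorations under Number of restorations and 150 in total under Materials and Methods. The original plan is 100. Since 150 − 100 = 50, the new cohort accounts for EsthetX HD restorations only, which agrees with the closed enrolment for the other two materials. The addendum's Study Design still speaks of materials placed in a single patient. That sentence and the Distribution of restorations section must be reconciled. On the counts, anyone who knows the cohort knows the material.

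**3. Do the retained safeguards hide it?** Separating placer from evaluator does not, because every addendum restoration is the same material. Calibration and consensus limit disagreement between evaluators, not an expectation they share. Similar appearance masks only where more than one material is possible. Photographs carry a subject number, but the addendum does not say whether its numbering reveals the cohort.

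**4. Which results are affected?** The comparison between materials is exposed to the difference in masking. The acceptance limits (for example, at most 10% C for color match) are absolute and apply to each material alone, so a difference between cohorts cannot bias them. Only knowledge of EsthetX HD itself could.

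**5. Sensitivity, not an estimate.** The plan's own figure is 50 placed so that 30 remain at 20% attrition. Inflating for attrition gives 30 / 0.80 = 37.5, or 38, so 50 is not reproduced. Forward, 50 × 0.80 = 40, which exceeds 30. The plan says its size follows a guideline, and the point does not depend on this figure.

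- With n = 40, one grade is 1/40 = 2.5 points and two grades are 5 points. The 10% limit is 4 restorations: 5/40 = 12.5% fails; 4/40 = 10% and 3/40 = 7.5% pass.
- Assume a true C rate p, and that a fraction m of true C grades is scored B. The spurious difference is p × m. The chance of meeting the limit is P(X ≤ 4), with X binomial (40, p(1 − m)) and restorations treated as independent. For p = 15%:

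| m | Scored C rate | Spurious difference (points) | P(X ≤ 4), n = 40 |
|---|---|---|---|
| 0 | 15.0% | 0 | 26% |
| 10% | 13.5% | 1.5 | 36% |
| 20% | 12.0% | 3.0 | 47% |
| 30% | 10.5% | 4.5 | 59% |
| 50% | 7.5% | 7.5 | 82% |

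- With n = 30 (limit 3), the corresponding chances are 32%, 41%, 51%, 61% and 82%.
- In the opposite direction, if a true rate of 10% were scored as 15%, the chance at n = 40 would fall from 63% to 26%.

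The values of p and m are assumptions; the documents supply neither.

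**The case against.** The strongest reply is that silence is not an open-label design. The addendum never says that evaluators know the material, and a reader might wrongly take that as documented. It is an inference from a single-material cohort: a strong one, but still an inference. This stands, and it is why the point is worded as no masking being described.

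Much of the rest also stands in part:

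- Independent scoring by calibrated evaluators who placed none of the restorations limits evaluator error, although it is not masking.
- Not every criterion is a soft judgement. Wear is measured in microns on casts, caries is present or absent, and C for marginal integrity or marginal discoloration has a physical anchor. Polishability is subjective but carries no acceptance limit.
- The analysis is descriptive, with no test between materials, so no error rate is inflated.
- The 5/40 example sits one restoration above the limit, where any single score flips the result. It shows that the sample is small, not how large evaluator bias is.
- The cohorts also differ in allocation, enrolment period, within-patient pairing and liner. Masking alone would not turn a difference into a material effect.
- Recoding casts and photographs does not reach the chairside scores to which the 10% limits apply.

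None of this removes the core. The plan requires a comparison across groups for which it describes different masking, and it neither addresses nor discloses this.

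**Conclusion.** The point holds in a limited form. As written, the addendum compares EsthetX HD, in a cohort whose membership reveals the material and for which no masking is described, with two materials assessed double blind under codes. Part of any described difference could come from assessment conditions. Neither its direction nor its size can be derived from the documents. The shift of one or two grades (2.5 to 5 points at n = 40) and the table above show only how sensitive the rates are under assumed values.

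A reader might infer that the difference in masking between cohorts biases the pass or fail result on the 10% limits. The documents do not support that, because each limit is applied to one material without reference to the others. For those limits the concern is only that evaluators may know they are scoring EsthetX HD. A reader might also infer that masked cast and photograph readings should replace the direct scores. They should not: the direct assessments are the plan's primary variables, and occlusal contact is a secondary one.

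**What to change.** - **Casts and photographs.** Have the coordinator recode the casts and photographs of all three materials into one numbered series. Read them in mixed order, without material or cohort, for wear, proximal contact and contour, and occlusal contact. Both cohorts' schedules already collect these items.
- **Direct scores.** Give evaluators sheets that show only a neutral study ID and the tooth number.
- **Reporting.** State in the addendum who is masked and how. Keep the direct assessments as primary, and report the chairside comparison with EsthetX HD as possibly unmasked and non-randomised.

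The cost is coordinator time and a revised sheet, with no new visits or procedures. The documents do not say who reads the casts, so the plan should name that role. Masking of the direct scores remains partial: original subjects have two study teeth and addendum subjects one or two, so evaluators may still guess the cohort. The gain is that wear and contact readings no longer depend on knowing the material. The other differences between the cohorts remain.
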